CD = cluster of differentiation; ELISA = enzyme-linked immunosorbent assay; IFN γ = interferon gamma; IL = interleukin; MSD = meso scale discovery; PBMC = peripheral blood mononuclear cell; RBD = receptor-binding domain; RNA = ribonucleic acid; S = Spike protein; SARS-CoV-2 = severe acute respiratory syndrome coronavirus-2; Th = T helper; TNF α = tumor necrosis factor alpha; VNA = virus neutralization assay

BIOMARKER EVALUATIONS

For participants with a positive test result for SARS-CoV-2 infection, blood will be drawn for evaluation of biomarkers (eg, those associated with severe COVID-19), 28 days after symptom onset.

SAFETY EVALUATIONS

After each vaccination, participants will remain under observation at the study site for at least 1 hour to monitor for the presence of any acute reactions and solicited events. Participants will be asked to note in the diary occurrences of injection site pain/tenderness, erythema and swelling at the study vaccine injection site daily for 7 days post vaccination (day of vaccination and the subsequent 7 days).

Participants will be instructed on how to record daily temperature using a thermometer provided for home use. Participants should record the temperature in the diary in the evening of the day of vaccination, and then daily for the next 7 days approximately at the same time each day. Participants will also be instructed on how to note signs and symptoms in the diary, on a daily basis, for 7 days post vaccination (day of vaccination and the subsequent 7 days), for the following events: fatigue, headache, nausea, and myalgia.

- AEs and special reporting situations, whether serious or non-serious, that are related to study procedures or that are related to non-investigational sponsor products will be reported from the time a signed and dated ICF is obtained until the end of the study/early withdrawal. All other unsolicited AEs will be reported for each vaccination from the time of vaccination until 28 days post vaccination. All SAEs and AEs leading to discontinuation from the study/vaccination (regardless of the causal relationship) will be reported from the moment of first vaccination until completion of the participant's last study-related procedure.

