- i. Investigator must check for acute illness or body temperature ≥38.0°C/100.4°F at the time of vaccination. If any of these events occur at the scheduled time for vaccination, the vaccination can be rescheduled as long as this is in agreement with the allowed windows. If the vaccination visit cannot be rescheduled within the allowed window or the contraindications to vaccination persist, the sponsor should be contacted for further guidance. The investigator should also check if any other reasons, as listed in Section 7.1, Discontinuation of Study Vaccination, have been met and would prevent further study vaccination.
- j. For women of childbearing potential only. Only women who are postmenopausal as defined in Section 5.1.1 (see Inclusion Criterium 6a) or who have had their uterus removed are of non-childbearing potential. All other women are considered of childbearing potential.
- k. In a subset of participants in Groups 1-6.
- 1. Participants will be closely observed for a minimum of 1 hour post-vaccination. Any solicited local (at injection site) and systemic AEs, unsolicited AEs, SAEs, concomitant medications, and vital signs will be documented by study-site personnel following this observation period and participants will be allowed to leave the study site after it is documented that the 1-hour post vaccination observation period is complete.
- m. AEs and special reporting situations that are related to study procedures or that are related to non-investigational sponsor products will be reported from the time a signed and dated ICF is obtained until the end of the study/early withdrawal. All other unsolicited AEs and special reporting situations will be reported for each vaccination from the time of vaccination until 28 days post vaccination.
- n. All SAEs related to study procedures or non-investigational sponsor products will be reported for all participants from the time a signed and dated ICF is obtained until the end of the study/early withdrawal. All other SAEs are to be reported for all participants from the moment of first vaccination until completion of the participant's last study-related procedure. Applicable from the time of local approval of protocol Amendment 5 onwards: Suspected AESIs are to be reported from the moment of vaccination until completion of the participant's last study-related procedure (see Section 8.3.1).

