All SAEs and AEs leading to discontinuation from the study/vaccination (regardless of the causal relationship) are to be reported for all participants from the moment of first vaccination until completion of the participant's last study-related procedure, which may include contact for safety follow-up. The sponsor will evaluate any safety information that is spontaneously reported by an investigator beyond the time frame specified in the protocol.

All AEs will be followed until resolution or until clinically stable.

Adverse Events of Special Interest

From the time of local approval of protocol Amendment 5 onwards, TTS is considered to be an AESI. Suspected AESIs (thrombotic events and thrombocytopenia [defined as platelet count below $150,000/\mu L^0$]) will be recorded from the moment of vaccination until the end of the study/early withdrawal. An AESI Adjudication Committee with appropriate expertise will be established to evaluate each suspected AESI and determine whether it is a case of TTS. (see Section 8.3.6).

Serious Adverse Events

All SAEs, as well as PQC, occurring during the study must be reported to the appropriate sponsor contact person by study-site personnel within 24 hours of their knowledge of the event.

SAEs, including those spontaneously reported to the investigator, must be reported using an SAE form. The sponsor will evaluate any safety information that is spontaneously reported by an investigator beyond the time frame specified in the protocol.

Information regarding SAEs will be transmitted to the sponsor using the Serious Adverse Event Form and Safety Report Form of the CRF, which must be completed and reviewed by a physician from the study site and transmitted to the sponsor within 24 hours. The initial and follow-up reports of an SAE should be transmitted electronically or by facsimile (fax). Telephone reporting should be the exception and the reporter should be asked to complete the appropriate form(s) first.

Adolescents

Signs and symptoms of Multisystem Inflammatory Syndrome in Children (MIS-C) will be monitored and reported as SAE in children with (suspected) COVID-19 as confirmed by a positive RT-PCR result for SARS-CoV-2, and in children of mothers or close relatives with prior (within 4-weeks) or current suspected or confirmed COVID-19. Further details on case definition and reporting of MIS-C in children can be found in section 10.12.

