5.6.1. Adverse Events

5.6.1.1. Definitions

Solicited AEs shown in the tables are extracted from the investigator assessment pages (CE) of the CRF. For unsolicited AEs, only the AEs within the 28-day period following each vaccination will be presented in the safety tables except for SAEs, which will be captured and tabulated in the outputs covering the whole study period. All other collected unsolicited adverse events will be presented through listings.

Solicited administration site symptoms will be considered as related to the study vaccine (by definition).

The severity of the AEs will be classified as grade 1 to 4. Solicited events that are graded less than grade 1, are not considered as AE. In case no grades are available, the grading of the solicited events will occur according to the grading list in Appendix 3.

For AESI, the following is defined:

- Suspected AESI : as reported by investigator and presented by: Embolic and thrombotic events (SMQ) + PT; Haematopoietic thrombocytopenias (SMQ) (broad) or HLT Thrombocytopenias + PT; Other SMQ + PT.
- Suspected AESI: Embolic and thrombotic events (SMQ), Haematopoietic thrombocytopenias (SMQ) (broad) or HLT Thrombocytopenias and presented by: Embolic and thrombotic events (SMQ) + sub-SMQ1 + PT; Haematopoietic thrombocytopenias (SMQ) (broad) or HLT Thrombocytopenias + PT;
- Qualified for assessment AESI: [Embolic and thrombotic events (SMQ)] and [Haematopoietic thrombocytopenias (SMQ) (broad) or HLT Thrombocytopenias or platelet count below normal ranges per local or central laboratory report or platelet count < 150 × 10⁹/L] and presented by: Embolic and thrombotic events (SMQ) + sub-SMQ1 + PT;

^a As indicated previously, all analyses, including the safety analyses, will be conducted by actually received vaccine (“as treated” principle). The sentence “by study intervention regimens as designed per protocol” indicates that the statistical tables are designed with the planned vaccine regimens as columns. Therefore, participants who receive e.g. “Placebo, Placebo” instead of “Ad26.COV2.S 5x10¹⁰ vp, Placebo” will appear in the “Placebo, Placebo” column. However, to avoid sparse columns, participants who receive e.g. “Placebo, Ad26.COV2.S 5x10¹⁰ vp” (which is not a planned vaccine regimen) will be excluded from the statistical tables. They will be included in the listings, as well as in the programmed patient narratives where they will appear as “Subjects with vaccine misallocation”.

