5.6.1.2. Analysis of Adverse Events

Number and percentage of participants with at least one particular AE (unsolicited/solicited) will be tabulated. Unsolicited AEs will be summarized by System Organ Class and Preferred Term. Solicited AEs will be summarized by class (administration site/systemic) and Preferred Term.

For solicited AEs following tables will be provided: summary, by worst severity grade, at least grade 3, related (systemic only), time to onset (in days) and duration (in days) for most frequent events and body temperature. Note: Duration is defined as number of days from the start of the event until resolution of the event. The time to first onset is defined as (date of first onset – reference date + 1). The reference date is the start date of the vaccination period.

For unsolicited AEs, the following tables will be provided: summary table (including SAE, fatal outcome, and discontinuation), all events, most frequent, at least grade 3, permanent stop of vaccine, related, and SAE.

As a general remark, COVID-19 cases will be analyzed separately (see section 5.7.3).

- SAEs that are COVID-19 related will not be included in the SAE tables, but will be included and flagged in the SAE listings. In MedDRA version 23.0, Preferred Terms (PT codes) “COVID-19 (10084268)”, “COVID-19 pneumonia (10084380)”, “Suspected COVID-19” (10084451), and “Asymptomatic COVID-19 (10084459)”, “Coronavirus infection” (10051905), “Severe acute respiratory syndrome” (10061982), “SARS-CoV-2 carrier” (10084461), “Exposure to SARS-CoV-2” (10084456) and “Occupational exposure to SARS-CoV-2” (10084394) will be considered COVID-19 related AEs^a.

Listings and/or participant narratives will be provided as appropriate, for those participants who die, discontinue study vaccinations due to an AE, or experience a severe or serious AE.

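### The SAP tables of AEs leading to discontinuation leave out non-serious AEs that start more than 28 days after a dose, although the protocol has them reported to the end of participation

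*SAP*

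**What the plan says.** **Collection.** Protocol 8.3.1 states: "All SAEs and AEs leading to discontinuation from the study/vaccination (regardless of the causal relationship) are to be reported for all participants", from first vaccination to the participant's last study-related procedure. The synopsis has the same rule: "All SAEs and AEs leading to discontinuation from the study/vaccination (regardless of the causal relationship) will be reported from the moment of first vaccination". Seriousness is not a condition in either place.

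**Schedule of Activities footnotes.** Footnote m of 1.3.1, repeated in the other schedules, says: "All other unsolicited AEs and special reporting situations will be reported for each vaccination from the time of vaccination until 28 days post vaccination". Footnote n extends reporting for serious events: "All other SAEs are to be reported for all participants from the moment of first vaccination until completion of the" participant's last procedure. It treats suspected AESIs similarly. AEs leading to discontinuation are not named.

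**Tabulation.** SAP 5.6.1.1 says: "For unsolicited AEs, only the AEs within the 28-day period following each vaccination will be presented in the safety tables except for SAEs". For the rest: "All other collected unsolicited adverse events will be presented through listings". SAP 5.6.1.2 then lists the unsolicited-AE tables: "summary table (including SAE, fatal outcome, and discontinuation), all events, most frequent, at least grade 3, permanent stop of vaccine, related, and SAE". It attaches no exception for the discontinuation outputs.

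**Periods.** SAP 5.6.1.3 assigns an AE to a period by its start date and time. SAP 5.1.2 (Table 1) closes each post-dose period at the end of the 28th day after the vaccination day. It describes the combined whole-study period for SAEs only.

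**The concern.** An AE that stops vaccination is of interest because of what it led to, whenever it began. Protocol 7.1 reflects this: a related AE, worsening health or intercurrent illness can end vaccination with no time limit after the previous dose. Protocol 9.4.2 says that all reported AEs enter the analysis. SAP Appendix 2, which records changes from the protocol-planned analyses, does not declare this restriction.

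Take a non-serious AE that starts on Day 40 in a 56-day arm and leads the investigator to withhold Vaccination 2. It is reportable under 8.3.1, yet it is outside the table whose purpose is to show such events by System Organ Class and Preferred Term. A reader of the clinical study report would take that table as complete, and it is not.

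**Working it through.** The plan states no count or rate for these events, so there is no plan figure to reproduce beyond the dosing days. The check is which days the tables cover.

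**Inputs**
- Vaccination 1 on Day 1; Vaccination 2 on Day 57 (Groups 1-6), Day 29 (Groups 7-8) and Day 85 (Groups 9-10): Protocol 6.1.
- Injection 3 on Day 169, Day 141 and Day 197 respectively: Protocol Tables 4 to 6.
- Post-dose period ends on vaccination day + 28: SAP 5.1.2.
- Actual Vaccination 2 timing in Groups 7-8, apart from 2 participants: 51 to 72 days after Vaccination 1: SAP Appendix 2.

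**Formulas**
- Uncovered days before Vaccination 2 (V2) = (V2 − 1) − (1 + 28), not less than 0.
- Uncovered days between Vaccination 2 and Injection 3 (I3) = (I3 − 1) − (V2 + 28).

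**Results on the planned schedule**

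| Schedule | Before Vaccination 2 | Vaccination 2 to Injection 3 | Vaccination 1 to Injection 3 |
|---|---|---|---|
| 56-day | 56 − 29 = 27 of 56 (48%) | 168 − 85 = 83 of 112 (74%) | 110 of 168 (65%) |
| 84-day | 84 − 29 = 55 of 84 (65%) | 196 − 113 = 83 of 112 (74%) | 138 of 196 (70%) |
| 28-day (planned only) | 28 − 29, so 0 of 28 | 140 − 57 = 83 of 112 (74%) | 83 of 140 (59%) |

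For Groups 7-8 as actually vaccinated, the gap before Vaccination 2 is 51 − 29 = 22 days to 72 − 29 = 43 days.

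**Scale, by assumption only.** Suppose the risk of a non-serious AE leading to a stop is constant over time and totals q over 196 days, with q between 1% and 5%. Risk over d days is 1 − (1 − q)^(d/196). The tables cover 58 days in both schedules (168 − 110 and 196 − 138), which gives 0.3% to 1.5%.
- 84-day arm: true risk 1.0% to 5.0%, so 0.7 to 3.5 points are missed, or 0.35 to 1.75 participants in 50.
- 56-day arm: true risk 0.86% to 4.30%, so 0.56 to 2.79 points are missed, or 0.42 to 2.10 participants in 75.

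Neither q nor the constant rate comes from the documents. The calculation shows only that the expected count per arm would be about two participants or fewer across that range.

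**The case against.** The strongest reply is that the information is not lost and the affected class is narrow. Much of this stands.

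- **Completion is shown elsewhere.** SAP 5.2 counts participants who discontinued vaccination or the study, with reasons for termination, by regimen and throughout the study. SAP 5.6.1.2 also plans listings or narratives for AE-driven vaccine stops. A reader might infer that longer-interval regimens will look falsely easier to complete. The documents do not support that, because a Day 40 stop still counts in the disposition table. What that table does not promise is the AE term.
- **There is no randomised 28-day comparator in the safety tables.** Only 2 participants in Groups 7-8 kept the 28-day interval, and they appear in listings only. The others are analysed with Groups 1 and 6 (SAP Appendix 2). The live randomised contrast is 56 versus 84 days, where overall uncovered time is 65% versus 70%. Most of that gap is the 83 days common to all arms.
- **Uncovered days are not missed events.** A reader might infer that half to two thirds of stops before Vaccination 2 will be absent. That needs a constant event rate, and the documents give no rate at all.
- **Many events are unaffected.** SAEs are exempt (COVID-19-related SAEs are handled separately). AEs that start within 28 days and lead to a stop later stay in the table, because allocation is by start date.
- **Collection is largely covered.** The footnotes omit the category; they do not exclude it. Section 8.3.1 and the synopsis state the rule, and footnote n refers sites to 8.3.1. That section also has late-onset AEs recorded if they are still ongoing at the next vaccination.
- **Discontinuation AEs are not a listed primary endpoint,** and the safety analysis is descriptive.

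None of this changes what the two outputs would count. Under the SAP text they are incomplete by rule.

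**Conclusion.** The point holds as a mismatch between what the protocol collects and what the SAP tabulates. The vaccine-stop table and the discontinuation row would omit non-serious AEs that start more than 28 days after a dose and lead to a stop.

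The exposure left uncovered is certain on the planned schedule. It is about half of the time before Vaccination 2 in the 56-day arms, about two thirds in the 84-day arms, and about three quarters of the time from Vaccination 2 to Injection 3 in all arms. The number of events left out is unknown and may be small. This reading assumes that the 28-day limit in SAP 5.6.1.1 applies to every unsolicited-AE table in 5.6.1.2, as the text says.

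The larger uncovered share in the 84-day arm is a per-participant statement. In planned person-days, a 75-person 56-day arm leaves more uncovered (75 × 110 = 8,250) than Group 9 (50 × 138 = 6,900). The documents support neither a claim of interval bias in regimen completion nor a stated fraction of missed stops. The footnote wording is a secondary alignment matter.

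**What to change.** **SAP 5.6.1.1:** extend the exception so that it reads, in substance, except for SAEs and AEs leading to discontinuation of vaccination or study, which are tabulated over the whole study period. The whole-study period that SAP 5.1.2 describes for SAEs can be used, with the censoring at unblinding in SAP section 4 applied in the same way.

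**Protocol Schedule of Activities footnotes** (1.3.1 m/n; 1.3.2 and 1.3.3 l/m; 1.3.4 i/j; 1.3.5 l/m; 1.3.6 i/j): name AEs leading to discontinuation among the events reported until the last study-related procedure, to match 8.3.1.

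**Cost:** one clause in the SAP and one in the footnotes. There is no new data requirement and no change to how participants are managed. The reported rates of AEs leading to discontinuation may look slightly less favourable.

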Regimen	2	Cross Vaccination	2	Date and time of Cross Vaccination	Minimum of: a) 23:59 at the date of last contact (for early discontinuation) b) 23:59 at the date of database cut-off date in case of interim analysis c) 23:59 on Day 28 after the Cross Vaccination 1 (23:59 of day of booter vaccination + 28 days)
Follow-up 2	4			One minute after Cross Vaccination period end	Minimum of: a) 23:59 at the Date of last contact (for early discontinuation) b) 23:59 at the date of database cut-off date in case of interim analysis c) 23:59 at the Date of last visit

Note: the end date of the regimen phase should be the end date of the last post-dose period.

Adverse Events and selected other tables may display AEs (or other counts) by period. For such tables, active periods can be combined and additionally displayed. The active periods can be:

- “Post-Dose 1”
- “Post-Dose 2”
- “Post-Dose 1 and Post-Dose 2 Combined”, which refers to the “primary regimen”
- “Post- Antigen presentation or Placebo”
- “Post-Dose 1, Post-Dose 2 and Post-Antigen presentation or Placebo”, which refers to the complete regimen including Antigen presentation. It includes the 28-day period after each vaccination (dose 1, dose 2, Antigen presentation).

The primary endpoints include SAEs from the first vaccination until end of the study. This will be a combined period of post-dose 1, post-dose 1 Follow-up (FU), post-dose 2, post-dose 2 FU, post-Antigen presentation or Placebo and post-Antigen presentation or Placebo FU. This period will be labeled “Entire Period” or similar in the outputs.

The secondary endpoints include SAEs from the antigen presentation until end of the study. This will be a combined period of post-Antigen presentation or Placebo and post-Antigen presentation or Placebo FU. This period will be labeled “Entire Antigen Presentation Regimen” or similar in the outputs.

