5.3. Primary Endpoint(s) Analysis

The primary endpoints in this study, are:

Adults

Humoral Immune Response

All participants in groups 1-3 (3 dose levels of Ad26.COVS.S administered as a 2-dose schedule at a 56-day interval):

- Serological response to vaccination as measured by virus neutralization assay (VNA) titers and enzyme-linked immunosorbent assay (S-ELISA EU/mL), 28 days after Vaccination 2.
- Antibody geometric mean titers (GMTs) (VNA) and geometric mean concentrations (GMCs) (S-ELISA), 28 days after Vaccination 2.

All participants in groups 4-5 (2 dose levels of Ad26.COVS.S administered as a single vaccination):

- Serological response to vaccination as measured by VNA titers and ELISA (S-ELISA EU/mL), 28 days after Vaccination 1.
- Antibody GMTs (VNA) and GMCs (S-ELISA), 28 days after Vaccination 1.

All participants in groups 7-9 (5×10^{10} vp dose level, administered as a 2-dose schedule at a 28-day and at an 84-day interval):

- Serological response to vaccination as measured by VNA titers and ELISA (S-ELISA EU/mL), 28 days after Vaccination 2.
- Antibody GMTs (VNA) and GMCs (S-ELISA), 28 days after Vaccination 2.

Safety and reactogenicity of Ad26.COVS.S

- Solicited local and systemic AEs for 7 days after each vaccination.
- Unsolicited AEs for 28 days after each vaccination.
- Serious adverse events (SAEs) and adverse events of special interest (AESIs) throughout the study (from first vaccination until end of the study)

Adolescents

Safety and reactogenicity of Ad26.COVS.S

- Solicited local and systemic AEs for 7 days after vaccination.
- Unsolicited AEs for 28 days after vaccination.
- SAEs (incl. Multisystem Inflammatory Syndrome in Children [MIS-C]) and AESIs throughout the study (from first vaccination until end of the study).

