5.4. Secondary Endpoint(s) Analysis

5.4.1. Key/Confirmatory Secondary Endpoint(s)

The secondary endpoints in this study, are:

Adults

Anamnestic response to antigen presentation of Ad26.COV2.S at the 1.25×10^{10} vp dose level, administered 4 months after Vaccination 2 (2-dose schedule) or 6 months after a Vaccination 1 (single-dose schedule), 7 days after antigen presentation:

- Serological response to vaccination as measured by VNA titers and ELISA (S-ELISA, ELISA U/mL [EU/mL]), 7 days after antigen presentation.
- Antibody GMTs (VNA) and GMCs (S-ELISA), 7 days after antigen presentation.

Safety and Reactogenicity of antigen presentation of Ad26.COV2.S:

- Solicited local and systemic AEs for 7 days after antigen presentation

- Unsolicited AEs for 28 days after antigen presentation
- SAEs and adverse events of special interest (AESIs) throughout the study (from after antigen presentation until end of the study)

Humoral Immune Response across all groups, at all blood collection timepoints.

- Neutralizing antibody titers to the wild-type SARS-CoV-2 virus expressing S protein as measured by VNA, at all blood collection timepoints.
- Binding antibody titers to SARS-CoV-2 or individual SARS-CoV-2 proteins (e.g., S protein) as measured by ELISA, at all blood collection timepoints.

Adolescents

Humoral immune response to a single dose of Ad26.COV2.S at the 2.5×10^{10} dose level, administered IM.

- Serological response to vaccination as measured by VNA titers and ELISA (S-ELISA, EU/mL), 28 days after vaccination.
- Antibody GMTs (VNA) and GMCs (S-ELISA), 28 days after vaccination.

Humoral immune response to Ad26.COV2.S at the 2.5×10^{10} dose level, at all blood collection timepoints.

- Neutralizing antibody titers to the wild-type SARS-CoV-2 virus expressing S protein as measured by VNA, at all blood collection timepoints.
- Binding antibody titers to SARS-CoV-2 or individual SARS-CoV-2 proteins (eg, S protein) as measured by ELISA, at all blood collection timepoints.

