5.6.2. Laboratory, Vital Signs and Physical Examination

Laboratory safety parameters, change from baseline and change from pre-dose x over time will be tabulated. Abnormalities on the changes from reference, if available, will be categorized. Abnormalities will be tabulated by visit and by worst abnormality. Patient profiles will be provided.

A listing of all laboratory values will be made, restricted to participants with at least one laboratory abnormality.

Physical examination findings will be summarized at baseline. A listing of the abnormalities will be made.

Vital signs including temperature, pulse/heart rate, respiratory rate, and blood pressure (systolic and diastolic) will be summarized over time, using descriptive statistics. Abnormalities emerging after vaccination will be tabulated by worst abnormality grade using the FDA table in appendix 3.

An abnormality (toxicity grade or abnormality based on normal ranges) will be considered as emerging in a particular period if it is worse than the baseline value. If the baseline is missing, the abnormality is always considered emerging. A shift from ‘abnormally low’ at baseline to ‘abnormally high’ post baseline (or vice versa) is also emerging. In case a laboratory test result is censored (no numeric value is available, but only a verbatim term) then a numeric value will be imputed by a value exceeding the cut-off value with one unit. (<x: subtract 1 unit from x, >x: add 1 unit to x; <3.45 is imputed with 3.44).

In case no toxicity grades are defined for a test, the abnormalities (above/below normal range) will be used. In determining toxicity grades, the following rules are applied:

- worst grades/abnormalities are determined over the whole observational period for each trial period separately, including all post-baseline measurements of that period.
- The abnormalities ‘abnormally low’ and ‘abnormally high’ are considered equally important, i.e. if a participant has as well an abnormally low as an abnormally high value post-baseline, both abnormalities are shown in the tables. (This means that the sum of the percentages can be more than 100%)
- Note: as the grading scale for some parameters in the grading table has some gaps (zones where no toxicity grade definition exists), laboratory results falling in these zones will be allocated to the adjacent worst-case grade.

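### The SAP's whole-study safety tables name SAEs only, although AESIs to end of study, serious or not, are also a primary endpoint

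*SAP*

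**What the plan says.** **Endpoints.** SAP 5.3 lists for adults "Serious adverse events (SAEs) and adverse events of special interest (AESIs) throughout the study (from first vaccination until end of the study", and for adolescents "SAEs (incl. Multisystem Inflammatory Syndrome in Children [MIS-C]) and AESIs throughout the study (from first vaccination until end of the study". SAP 5.4.1 adds for adults "SAEs and adverse events of special interest (AESIs) throughout the study (from after antigen presentation until end of the study". Protocol 8.3.6 requires AESIs to be reported whatever their seriousness. Protocol 8.3.6.1 makes a platelet count below 150,000/μL enough for a suspected case.

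**Periods.** SAP 5.1.2 introduces its combined period *Entire Period* with "The primary endpoints include SAEs from the first vaccination until end of the study", and *Entire Antigen Presentation Regimen* with "The secondary endpoints include SAEs from the antigen presentation until end of the study". Neither sentence mentions AESIs.

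**Tables.** SAP 5.6.1.1 states: "For unsolicited AEs, only the AEs within the 28-day period following each vaccination will be presented in the safety tables except for SAEs". SAEs are tabulated over the whole study, and all other unsolicited events go to listings. The same section then defines three AESI categories by MedDRA grouping and preferred term, without giving a period. SAP 5.6.1.2 names the unsolicited-AE tables as "summary table (including SAE, fatal outcome, and discontinuation), all events, most frequent, at least grade 3, permanent stop of vaccine, related, and SAE".

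**Censoring.** SAP 4 ends the safety analyses at unblinding or at receipt of a COVID-19 vaccine outside the study, whichever is first. Later events are listed.

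**The concern.** The endpoint sections pair SAEs with AESIs over the whole study. The sections that turn endpoints into tables carry only the SAE half. Thrombosis with thrombocytopenia syndrome (TTS) is an important identified risk of this vaccine (protocol 2.3.1), and it is the reason AESIs were added to the endpoints. A reader who expects the primary AESI endpoint to be counted to end of study, before censoring, would find that the stated table rule does not deliver that count for non-serious events.

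**Working it through.** The plan gives no figure to reproduce here. The check sets the provisions side by side and then runs one event through them.

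| Provision | SAE | Non-serious AESI |
|---|---|---|
| Primary endpoint to end of study (SAP 5.3) | yes | yes |
| Adult secondary endpoint, antigen presentation to end of study (SAP 5.4.1) | yes | yes |
| Named in *Entire Period* (SAP 5.1.2) | yes | no |
| Named in *Entire Antigen Presentation Regimen* (SAP 5.1.2) | yes | no |
| Exempt from the 28-day table rule (SAP 5.6.1.1) | yes | no |
| Own table named (SAP 5.6.1.2) | yes | no |

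1. *Is every AESI an SAE?* No. Protocol 8.3.6 covers serious and non-serious events, and a modestly low platelet count need not meet any seriousness criterion in protocol 10.4.1.
2. *Is an AESI an unsolicited AE?* Yes. Protocol 8.3.2 makes unsolicited every AE that the diary does not ask about. The diary asks about pain/tenderness, erythema, swelling, temperature, fatigue, headache, nausea and myalgia.
3. *Where does the tabulated window end?* SAP 5.1.2 (phase definitions for Groups A-C) closes the post-dose period on the day of vaccination + 28 days: Day 1 + 28 = Day 29.
4. *Test event.* An adolescent in Group A has a platelet count just under 150,000/μL at about Day 85, recorded as a non-serious AE. Day 85 is after Day 29. It is before unblinding, which protocol 1.3.5 places at about 6 months (Day 169 in protocol Table 7). The event belongs to the primary endpoint. It is not an SAE, so under SAP 5.6.1.1 it goes to a listing.
5. *Which follow-up is exposed in adolescents?* At most Day 30 to about Day 168. This is a calendar ceiling and not surveillance time. Protocol 8.3.1 treats TTS as an AESI only from local approval of Amendment 5, although footnote m of protocol 1.3.5 has no such limit. No platelet count is scheduled for Groups A-C before unblinding, so a case would be found only incidentally.
6. *Which follow-up is exposed in adults?* None is established. AESI status starts at local approval of Amendment 5, and adult unblinding comes with implementation of the same amendment (protocol 6.4), after which SAP 4 sends events to listings. Before Amendment 5, non-serious AEs beyond 28 days were generally not collected (protocol 8.3.1).

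**The case against.** The strongest reply has five parts.

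- *The period is already stated.* SAP 5.3 and 5.4.1 give it in the endpoint definitions. This stands. A reader might infer that the SAP never says over what period AESIs count, but that would be wrong. The problem is a table rule that conflicts with the stated period.
- *AESIs have their own block in SAP 5.6.1.1.* It has a display hierarchy, and one category uses platelet counts from laboratory reports, which need not be AE records. The table list in 5.6.1.2 is headed as unsolicited AEs, so an AESI table's absence from it proves little. This makes it likely that a separate table is intended. The block still states no exemption from the 28-day rule in the same section and no whole-study period.
- *SAP 5.6 presents safety data over the entire antigen presentation regimen.* That partly covers the secondary endpoint, because SAP 5.1.2 gives almost the same label to a period that includes follow-up. SAP 5.6 does not name the *Entire Period*, which the primary endpoint needs.
- *Listings may be enough.* SAP 1 promises only limited adolescent outputs and leaves detail to the Data Presentation Specifications. Protocol 9.4.2 says summaries or listings for AESIs may be provided. With 33 participants, a listing can be counted by hand. This lowers the importance of the point, but none of these texts overrides the rule in 5.6.1.1.
- *Low platelet values appear elsewhere.* For laboratory data, SAP 5.6.2 says "Abnormalities will be tabulated by visit and by worst abnormality". A low value may therefore be visible there. The number of participants with the AESI would not be.

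**Conclusion.** The conflict is real and minor. On its wording, the SAP lists but does not count a non-serious suspected AESI that starts more than 28 days after vaccination and before unblinding, although that event falls within a primary endpoint. The version history records an AESI clarification in SAP version 3, so an incomplete update is a plausible explanation, though that is inference.

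The practical scope is mainly late, isolated, non-serious thrombocytopenia in the 33 adolescents before Amendment 6 unblinding. Serious AESIs are tabulated over the whole study. Protocol 2.3.1 puts TTS onset at about 1-2 weeks after vaccination, inside the tabulated window. Any affected event is still reported within 24 hours, adjudicated and listed.

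Two stronger readings are tempting. One is that TTS cases would be missed or that the adult safety conclusions are affected. The documents do not support this, for the reasons just given and because no affected adult time can be shown. The other is to express the gap as a large share of follow-up lost. Calendar days outside the 28-day windows include time before TTS became an AESI, time without platelet testing and, if counted to the last visit, time after censoring. No AESI rate is given, so no number of events follows.

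The conclusion assumes that AESIs are handled as unsolicited AEs and that the Data Presentation Specifications, which are not among the documents, do not already add the table. Local approval and implementation dates for Amendments 5 and 6 are not given.

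**What to change.** Three small edits:

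- SAP 5.6.1.1: extend the exception to *SAEs and (suspected) AESIs, serious or non-serious*.
- SAP 5.1.2: change *SAEs* to *SAEs and AESIs* in both sentences that introduce the end-of-study periods.
- SAP 5.6.1.2: name an AESI table over the *Entire Period*, and for adults also over the *Entire Antigen Presentation Regimen*, using the groupings already defined in 5.6.1.1.

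Keep the censoring at unblinding in SAP 4 as it is. Optionally, add AESIs to the listing and narrative criteria in SAP 5.6.1.2 to match protocol 9.4.2. The cost is a few words and one small table, with no new data and no change to trial conduct.
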